OCTOM	Office of Clinical Trials Operations and Management, NIDCR, NIH
OHRP	Office for Human Research Protections
OHRQoL	Oral Health-Related Quality of Life
OHSR	Office of Human Subjects Research
PBRN	National Dental Practice Based Research Network
PD	Protocol Deviation
PI	Principal Investigator
PO	Program Official, NIDCR, NIH
PS	Project Scientist, NIDCR, NIH

QA	Quality Assurance
QC	Quality Control
SAE	Serious Adverse Event/Serious Adverse Experience
SOP	Standard Operating Procedure
UP	Unanticipated Problem
US	United States

PROTOCOL SUMMARY

Title: Dental Implant Registry

Précis: Dental rehabilitation of partially and fully edentulous patients with endosseous implants has become a routine treatment modality, and it is estimated that up to 5 million dental implants are placed each year. There is a body of literature to suggest that biological and prosthetic complications occur, which may interfere with the health of the peri-implant tissues and the function and esthetics of the implant restoration. The purpose of this prospective, observational study conducted within the National Dental Practice-Based Research Network (PBRN) is to quantify the incidence of biologic and prosthetic complications and assess risk factors for implant complications.

Approximately 200 practitioners from 6 Regional Network Nodes will be recruited to enroll approximately 1550 patients with approximately 2000 implants for longitudinal observation. Patients will be enrolled at the time of implant prosthetic placement. Baseline patient demographic and characteristics, mucosal and prosthetic characteristic data and radiographic images taken for standard of care purposes will be obtained. Follow-up clinical data and standard of care radiographic images will be collected at 1, 2, and 3 years after prosthetic placement.

Objectives and Outcomes:

Primary objective: quantify the incidence of biologic and prosthetic complications amongst patients receiving dental implant therapy in a practice setting.

Primary outcomes: biologic (peri-implant mucositis, peri-implantitis, implant failure), and prosthetic complications that have compromised implant esthetics and/or function.

Secondary objectives:

- Determine risk factors for biologic and prosthetic complications amongst patients receiving dental implant therapy in a practice setting.
- Assess patient OHRQoL (Oral Health-Related Quality of Life) and satisfaction with esthetics and function following implant therapy.

Secondary outcomes: Patient, surgical, prosthetic risk factors; biologic and prosthetic complications, and OHRQoL.

[figure not shown]
Tertiary objectives:

- Explore the influence of prosthesis type on the incidence of prosthetic and biologic complications in a private practice setting.
- Explore factors predictive of patient OHRQoL (which includes satisfaction with esthetics and function).

Tertiary outcomes: Surgical and prosthetic factors; biologic and prosthetic complications, OHRQoL.

Population:	Approximately 200 National Dental PBRN practitioners from all six regional nodes will enroll approximately 1550 patients planned to undergo implant prosthetic placement to contribute approximately 2000 dental implants for longitudinal observation.
Study Duration:	Approximately 5 years
Subject Participation Duration:	Approximately 3 years for patients and approximately 4 years for practitioners
Estimated Time to Complete Enrollment:	Practitioner Enrollment = approximately 12 months Patient Enrollment = approximately 12 months

Schematic of Study Design:

2 INTRODUCTION: BACKGROUND INFORMATION AND SCIENTIFIC RATIONALE

2.1 Background Information

With the advent of osseointegration, dental rehabilitation of partially and fully edentulous patients with endosseous implants has become a routine treatment modality, and it's estimated that up to 5 million dental implants are placed each year.^{1, 2} While in many cases dental implants have been reported to achieve long-term success, they are not immune from complications associated with improper treatment planning, patient-related factors, surgical and prosthetic execution, material failure, and maintenance.³ The longitudinal survival rates of osseointegrated dental implants range between 90-96.2% after 5 years.³⁻⁵ These numbers represent implants that are present and in function but may not fully capture rates of peri-implant disease and/or health. There is a substantial body of literature to support that biological and prosthetic complications occur which may interfere with the health of the peri-implant tissues and the function and esthetics of the implant restoration⁶. Peri-implant diseases are classified into peri-implant mucositis, inflammation restricted to the peri-implant mucosa, and peri-implantitis, characterized by peri-implant bone loss.³ There is variability in the reported prevalence of peri-implant diseases. A systematic review of the literature of studies reported rates of peri-implantitis range from 10-47% of all implants in a time period ranging from 1 to 20 years.⁷⁻⁹ Rates of peri-implant mucositis have been observed in up to 64% of subjects with dental implants.⁹

The limitations of the current body of literature of biologic and prosthetic complications are based on many small studies and in large part conducted in academic and specialty settings. Many of these studies have been retrospective and may not accurately represent the setting of private practice. An example is the retrospective study of the PEARL (Practitioners Engaged in Applied Research and Learning) network of private practitioners, in which the implant failure, defined as excessive bone loss as measured on submitted radiographs, was 18.7% over a mean follow-up period of 4.2 years. Thus, the success rate in this study was lower than historic controls of studies conducted in academic or specialty settings.¹⁷ There is limited data available on the implementation of risk assessments in a practice setting and their impact on the prevention of peri – implant disease. There is an additional paucity of research to address other factors that can influence implant outcomes, such as implant design, implant surface characteristics, implant placement, loading protocols, occlusion and prosthesis design.¹⁹ Many of the previous retrospective studies that have examined implant outcomes have focused on survival data rather than success. There is a lack of studies evaluating the function, tissue health and patient satisfaction of implant systems in maintenance phase in community practices.

In orthopedics, significant improvement in the clinical practice and in the quality of care has been shown from the results of the national total joint replacement registry.^{20, 21} We will create an implant registry within the National Dental PBRN that will record the setting and implant therapy provided, the implants used, the prosthetic therapy provided and any complications. The purpose is to quantify the incidence of biologic and prosthetic complications and assess risk factors for and develop a risk assessment for implant complications. Better understanding of the complications and the risk factors associated with implants could lead to the development of clinical strategies and protocols for the prevention of adverse implant therapy outcomes.

2.2 Rationale

Prospective, longitudinal studies are needed to identify significant risk factors for peri-implant diseases. This will allow better information to be shared with practitioners and patients regarding possible complications, which seem to be common occurrences with a significant number of implant restorations.¹⁹ Furthermore, this could give practitioners relevant information to assist in treatment decisions that would improve outcomes.²⁰ It would also be a relevant addition to the implant literature to have information based on real-world dental care-delivery experiences rather than specialty or academic clinical studies.

The National Dental PBRN offers a great opportunity to gather data in a comprehensive manner on a large, diverse patient population, and therefore, the results may be

generalizable to a wide range of patients in a private practice setting. The registry will create opportunities for subsequent, additional targeted studies on specific complications available from the registry data. We expect that the results from this study could significantly impact the clinical practice of implant dentistry and the quality of care and satisfaction of patients.

2.3 Potential Risks and Benefits

This is an observational study. Research participants will not receive dental care or an intervention as a study procedure but will continue to receive routine clinical care as patients of the participating dentists. Risks of dental procedures provided as part of routine clinical care are not considered to be study-associated.

2.3.1 Potential Risks

As with any study, there is the possibility of breach of confidentiality. Appropriate precautions will be taken and procedures will be followed to maintain confidentiality. These include use of unique study codes for participants, encryption of electronic data for transmission to the coordinating center, and password-protected computers for data storage. Compliance with all IRB regulations concerning data collection, data analysis, data storage, and data destruction will be strictly observed.

2.3.2 Potential Benefits

Participation in the study will provide no direct benefit to participants. Benefits would accrue to society in enhanced understanding of implant complications and the associated risk factors. Thus, study results could enhance care for future patients through evidence-based recommendations for more timely and appropriate interventions and prevention of these complications.

3 OBJECTIVES AND OUTCOME MEASURES

3.1 Primary

Objective	Brief Description/Justification of Outcome Measure	Outcome Measured By	Time Frame

To quantify the incidence and prevalence of biologic complications amongst patients receiving dental implant therapy in a private practice setting.
	
Biologic complications will be defined as an implant that presented with measured bone loss on the radiographs and/or bleeding on probing, or failed implant. Biologic complications will be defined as a) Peri-implant mucositis: Bleeding on Probing (BoP) and/or purulent exudate without measured bone loss, or b) Peri-implantitis: measured bone loss on the radiographs, or c) Implant failure: an implant that has been lost or is planned to be removed
 
Incidence estimation will be based on a Poisson model for incidence per implant and year of follow-up.
	
a) The presence or absence of Bleeding on Probing (BoP) is measured by the practitioners at the annual evaluation visits and recorded in the annual follow-up surveys.
 
b) The radiographic bone changes are measured on the radiographs by calibrated examiners, utilizing the known geometry of the implant to convert to mm of bone change. Bone loss is defined as the negative change of the bone level measurements from the baseline radiographs taken at the time of prosthetic insertion.
 
c) Implant Failure: absence or planned removal of implant
	
Baseline data are collected at the time of prosthesis insertion and at each of the three annual follow-up visits.
 
The radiographs taken for clinical care purposes at prosthesis insertion and the 1, 2 and 3-year follow-up visits that are approved by the study team to be added to the radiograph repository will be utilized for radiographic assessments.

Objective	Brief Description/Justification of Outcome Measure	Outcome Measured By	Time Frame

To quantify the incidence and prevalence of prosthetic
	
Prosthetic complications will be defined as any complication that has compromised the esthetics
	
At baseline, practitioners will record surgical data (implant brand, size
	
Baseline surgical and specific prosthetics data


complications amongst patients receiving dental implant therapy in a private practice setting.
	
and/or function of the implant restoration.
 
Incidence estimation will be based on a Poisson model for incidence per implant and year of follow-up.
	
and diameter, surgical therapy and site development, healing complications) and prosthetic data (type of restorations, abutment, restorative material, and occlusal scheme). At follow-up, practitioners will collect clinical data and record the presence or absence of the following complications on the prosthetics data collection survey: loose or lost screw, screw fracture, structural fracture, resin or porcelain fractures, loss of retention, abutment/implant misfit.
	
will be collected at the insertion of the prosthesis. The annual follow-up surveys at years 1-3 will record the presence or absence of prosthetic complications.

--	--	---	---

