- Clinical examination of the prosthesis: Screw fracture, Screw loosening, Loss of screw, Structural fracture, Resin fracture, Porcelain fracture, Loss of retention, Loss of filling covering screw, Abutment/implant misfit, Abutment/prosthesis misfit, Cement remnants present, Wear of the occlusal surfaces.
- Radiographs: Practitioners will submit digital radiographs of each study implant, taken at baseline (after implant prosthetic placement) and at annual follow-up visits 1, 2, and 3 years following prosthetic placement. The radiograph should be void of any identifiers. Radiographs will be uploaded to the centralized study database provided by the NCC. Node Coordinators will review the radiographs and remove identifiers if present. The study team completes the final review to determine whether the radiograph is sufficient quality to be included in the radiograph repository. If the radiograph is insufficient quality, the study team will work with the Node Coordinator to provide feedback, if applicable, and determine whether a higher quality radiograph can be found. Radiographs in the radiograph repository will go through the adjudication process, where trained and calibrated evaluators assess the radiograph for quality and will determine peri-implant bone height measurements and prosthetic fit for each implant.

Patients

Patient questionnaires will ascertain patient satisfaction and OHRQoL thought to be important patient-reported outcomes. Patient satisfaction with function and esthetics will be measured with the OHRQoL.

Baseline: At the implant prosthetic placement visit, patients will complete the *Baseline Patient Demographics, Patient Contact Survey, Patient Characteristics Survey and Baseline Oral Health Quality of Life (ORHQoL) Survey*, which will ascertain information related to: 1) demographics, 2) socioeconomic variables, 3) medication use, 4) medical conditions, 5) satisfaction with function and esthetics prior to implant therapy, and 6) oral health quality of life prior to prosthetic implant therapy.

Annual follow-up: Patients will complete the *1-, 2-, or 3-Year Patient Annual Follow-Up Survey, which includes the OHRQoL survey and Patient Contact survey*, to ascertain patient information related to: 1) Contact information changes 2) Changes in health history, medications and smoking habits, 2) OHRQoL following prosthetic implant therapy.

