Bone height will be measured utilizing the known geometry of the implant to convert to mm of bone change. The evaluations will be used to provide confirmation of bone loss, which is defined as the negative change of the bone level measurements from the baseline radiographs taken at the time of prosthetic insertion. Alveolar bone levels will be measured at mesial and distal sites of study implants on all images as the distance between platform of the implant and alveolar bone crest. All measurements will be made in pixels. The unit pixel is merely a digital measurement unit and varies with the resolution with which the image was saved or scanned. For conversion back to millimeters, a known dimension needs to be represented on an image. The implant length or diameter will serve as known entity on the radiographs, and each implant will be measured. The custom conversion for each image utilizing the measured implant length in pixels by the known implant length or spacing between the threads in millimeters. This method allows for the comparison between images taken with different systems and makes the changes clinically relevant as they are expressed in millimeters. Image processing software will be used to capture measurements from the radiographic images.

Measurement of the emergence angle

The mesial and distal emergence angle of the prosthesis will be measured using the implant platform as the vertex, with one ray following the long axis of the implant and the other aligned with the gingival contour of the implant abutment.

Prosthetic fit

The presence of a gap between the abutment and the implant and/or the abutment and the prosthesis will be recorded.

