11.2 Sample Size Considerations

The primary objective of the study is descriptive (i.e., to determine the incidence of various outcomes among patients receiving dental implants). As such, a power analysis is based on the precision with which we can estimate the proportion of the occurrence of the primary outcomes (Peri-implant mucositis, Peri-implantitis) among all eligible patients. The study plan is to recruit approximately N=1550 patients with a total of approximately 2000 dental implants. In a published meta-analysis, the prevalence of Peri-implant mucositis was estimated to be 50% and the prevalence of Peri-implantitis was estimated to be around 20% within the three year follow-up period^{7,9,32}. To a good approximation, if W is the width of the 95% confidence interval (i.e., the confidence interval is of the form $P \pm W/2$) for an estimated proportion P based on N observations, then the number of participants (N) needed to achieve that width is given by

$$N = 16 * P * (1 - P) / (W^2) ,$$

where P and W are expressed on a fractional basis. For a given value of W, the formula above is symmetric about P=0.5 and W is largest for P=0.5. Table 1 and figure 1 show the different precision (i.e., width) of our estimated 95% confidence intervals as the underlying cumulative incidence of complications varies.

Table 1.

		width of the 95% confidence interval (W)	
expected 3-year prevalence and cumulative incidence of participant-level complications	N = 1400	N=800	N=500

20%	0.043	0.057	0.072
25%	0.046	0.061	0.078
30%	0.049	0.065	0.082
35%	0.051	0.067	0.086
40%	0.052	0.069	0.088
45%	0.053	0.070	0.089
50%	0.053	0.071	0.090

The secondary objective is to assess association between risk factors and the biologic and prosthetic outcomes. The primary outcomes are Peri-implant mucositis and Peri-implantitis. Based on the assumptions of equal category size, a cluster size of 1.4, and a prevalence of 50% for Peri-implant mucositis and 20% for Peri-implantitis in the reference group, table 2 presents the outcome prevalence values we can detect with varying degree of intracluster correlation coefficient (ICC).

Table 2.

Detectable outcome prevalence values		
ICC	Reference group outcome prevalence values = 50%	Reference group outcome prevalence values = 20%
0.1	56.43%	25.40%
0.2	56.55%	25.50%
0.3	56.67%	25.61%
0.4	56.78%	25.71%
0.5	56.90%	25.81%

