For biologic complications, three binary outcomes will be examined: Peri-implant mucositis, Peri-implantitis and implant failure. For prosthetic complications, six binary outcomes will be examined including loosening of screws, screw fracture, structural fracture, resin or porcelain fractures, loss of retention, and abutment/ implant misfit. For the primary analysis, all outcomes will be defined at the person level and will be binary (Y/N) regardless of the number of complications experienced per participant. The 3-year cumulative incidence will be calculated as a ratio, where the numerator will be the total number of persons with one or more new (not existing at baseline) complications by the end of the follow-up period, and the denominator will be the total number of persons at risk for that complication at baseline. The prevalence will be calculated using the total number of persons with a complication (both new and existing) divided by the total number of persons at risk during each time interval (baseline, year 1, 2, and 3). In addition, the incidence and prevalence will be computed separately by age group, DM, smoking status, medication use, Osteoporosis, Radiation therapy, Periodontitis diagnosis, and Gingivitis diagnosis. We will calculate incidence and prevalence for all complications except implant failure (incidence only). If data permits, we'll also examine the number and rates of repeated prosthetic complications and the disease progression in biologic complications (mm bone loss over time) for exploratory analysis.

Secondary Objectives. To examine risk factors for biologic and prosthetic complications among patients receiving dental implant therapy in a private practice setting.

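### Any negative change from the baseline film counts as bone loss, with no margin for measurement error and no site rule, so reading error alone would label most stable implants peri-implantitis over three years

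*Protocol*

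**What the plan says.** Section 3.1 defines three biologic complications: mucositis, peri-implantitis and implant failure. Peri-implantitis is radiographically measured bone loss; bleeding or exudate is not required. Bone loss is then fixed in the same table: "Bone loss is defined as the negative change of the bone level measurements from the baseline radiographs taken at the time of prosthetic insertion". Section 7.3 repeats the rule: "which is defined as the negative change of the bone level measurements from the baseline radiographs". Neither place gives a minimum change.

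Mucositis is the complement among inflamed implants: "Bleeding on Probing (BoP) and/or purulent exudate without measured bone loss".

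On measurement, section 7.3 says: "Alveolar bone levels will be measured at mesial and distal sites of study implants on all images". Readings are in pixels and are converted to mm from a known implant dimension. No rule says whether the mean, the worse site or either site decides. Section 7.1 has radiographs "taken at baseline (after implant prosthetic placement) and at annual follow-up visits 1, 2, and 3 years following prosthetic placement", so one baseline film is compared with up to three later ones. The films are those taken for clinical care.

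In section 11.3 the numerator of the three-year cumulative incidence is the "total number of persons with one or more new (not existing at baseline) complications by the end of the follow-up period". Section 11.2 plans on a published figure: "the prevalence of Peri-implantitis was estimated to be around 20" per cent.

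**The concern.** A difference between two noisy readings is almost never exactly zero. If the sign alone decides, an implant with no bone change is positive about half the time, and each further film gives another chance. Better reading does not help: a smaller error SD shrinks the differences but leaves the share of negative ones unchanged.

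The rule underlies two of the three primary biologic outcomes, Hypothesis 1 (a 50% three-year incidence of any biologic complication) and the biologic risk-factor models. A stable implant that does not bleed still enters the numerator, because a negative reading is enough. The mucositis definition excludes measured bone loss, so an error in one outcome carries over to the other.

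**Working it through.** **1. The plan's own figures.** Table 1 uses W = √(16·P·(1−P)/N). For P = 0.20, N = 1400: √(2.56/1400) = 0.0428 (stated 0.043). For P = 0.50: √(4/1400) = 0.0535 (stated 0.053). Table 2, first row, is reproduced with 1400 × 1.4 = 1960 implants in two equal groups, design effect 1 + 0.4 × 0.1 = 1.04, two-sided 0.05 and 80% power (implant total and power are assumed). This gives 56.44% and 25.40%, against 56.43% and 25.40% stated. The tables are sound; the problem is the outcome that they are applied to.

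**2. False positives for a stable implant.** Inputs: no true change; symmetric, independent, continuous image errors; one site or the mean of two; k follow-up films. All k + 1 readings are exchangeable. The implant escapes a positive call only if baseline is the lowest reading, which has probability 1/(k + 1). So P(ever positive) = k/(k + 1):

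| Follow-ups read | P(ever positive) |
|---|---|
| 1 | 50% |
| 2 | 67% |
| 3 | 75% |

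The error SD does not appear. Simulation gave 0.50 and 0.75 for one and three visits at SDs of 0.1 to 0.5 mm.

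**3. Recording to 0.1 mm, ties counted as no loss.** The protocol gives no SD, so 0.1 to 0.5 mm is assumed. Simulated three-visit figures:
- mean of sites, then rounded: 54 to 71%
- one site: 60 to 72%
- sites rounded, then averaged: 65 to 73%

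**4. Either site counts.** With independent site errors, 1 − (1/4)² = 94% over three visits. At between-site error correlations of 0.5 and 0.8, simulation gives about 89% and 84%.

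**5. Person level.** 2000/1550 = 1.29 implants per patient. If 71% have one implant and 29% have two, with independent errors: 0.71 × 0.75 + 0.29 × (1 − 0.25²) = 0.80. About 80% of patients with only stable implants would be counted, against 50% in Hypothesis 1.

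**6. Against the 20% planning value.** If 20% of implants truly lose bone and all are detected, the apparent rate is 0.20 + 0.80 × 0.50 = 60% at one visit and 0.20 + 0.80 × 0.75 = 80% over three.

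**7. Mucositis.** At one visit, half of stable bleeding implants are read as bone loss and leave the mucositis category. For a stable implant bleeding at all three visits, P(never labelled mucositis) = P(baseline is the highest of four readings) = 1/4.

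**8. Risk factors.** Take Table 2's 20% versus 25.40%, full sensitivity, and the same false-positive rate in both groups. Effective n per group is 980/1.04 = 942.
- Rate 75%: 80.0% versus 81.35%; SE = √((0.160 + 0.152)/942) = 0.0182; 0.0135/0.0182 = 0.74; power about 12%.
- Rate 50%: 60.0% versus 62.7%; SE = 0.0224; 0.027/0.0224 = 1.20; power about 23%.

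**9. What a threshold buys.** With the smallest detectable change, 1.96·√2·SD, as threshold, simulated false positives are:

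| Setting | One visit | Three visits |
|---|---|---|
| One site | 2.5% | 6% |
| Worse site, independent errors | 4.9% | 12.1% |
| Worse site, correlation 0.8 | 3.9% | about 9.5% |

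If the threshold uses reader SD only, and films differ by a further between-film SD of the same size (assumed), the three-visit figures rise to about 18.5% (one site) and 30 to 34% (worse site).

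**The case against.** The best defence is that the negative change only states a direction and that a cut-off will come in the SAP or a manual. That would be fair if the protocol were silent. It is not: it gives a definition twice, and peri-implantitis rests on it alone. A later cut-off would change the outcome as the protocol states it.

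A second defence is duplicate reading with a third evaluator and a panel (section 7.3). This controls disagreement about one film, to a limit not given. It sets no margin for change between films.

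Other objections stand and limit the point:

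- A reader might infer that 94% of stable implants would be misclassified. That needs an either-site rule, which the protocol does not state, and independent errors, although both sites share one film and one scale conversion. It also needs all four films, and section 4 allows that some patients will not complete every visit.
- Most applies to the three-year measure. At one visit the figure is half. Recording to 0.5 mm with a small error would fall below half over three visits (mean of sites), but the protocol describes no such rounding.
- A reader might infer that mucositis is under-counted overall. The shift holds at each visit, but an implant can qualify at another visit and no net effect on the ever/never measure is shown.
- A reader might infer that associations are always diluted. That needs non-differential error. The number of readable films may vary with patient or practitioner, and emergence angle and prosthetic fit are risk factors read from the same films.
- A bleeding implant with no readable film could literally be said to have no measured bone loss. The documents do not say it would be classed that way, and section 11.3 plans multiple imputation for missing outcomes.

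**Conclusion.** The concern holds for the missing margin and the missing site rule. Followed as written, the definition labels a stable implant peri-implantitis with probability 50% at one visit and 75% over three (about 54 to 73% with 0.1 mm recording). This assumes no true change, symmetric and independent image errors, and one site or the mean of two. The three-year incidence of peri-implantitis and of any biologic complication would be driven largely by reading error and would not correspond to the 20% planning rate. At any one visit about half of stable bleeding implants would move from mucositis to peri-implantitis. Risk-factor associations would be weakened if the error is non-differential.

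The definition should be corrected before outcomes are analysed.

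**What to change.** In sections 3.1 and 7.3:

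1. Count bone loss only when the change from baseline exceeds a threshold in mm, fixed before outcome analysis.
2. State the site rule: mean, or worse of mesial and distal.
3. Set the threshold above the smallest detectable change for that site rule. The duplicate readings give the reader component only. They omit projection and scaling differences between films, so treat the result as a lower bound and add a stated allowance.
4. Use the same threshold in the mucositis definition.
5. State that implants without a readable baseline and follow-up film are missing for both outcomes and enter the missing-data handling of section 11.3.
6. Show one or two larger thresholds as sensitivity analyses.

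The cost is protocol wording and a reproducibility calculation on readings already planned; no new visits or films are needed. The downside is that small true losses drop out of the binary outcome, but the planned mixed model for mm bone loss keeps them.
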